**For aim 5:**

*The primary outcome measure* consists of investigating the differences between treatment conditions in oxytocin plasma concentration in ASD. Samples of post-administration of IN-OT will be analyzed. We will conduct ANOVA repeated measures on the different OXT concentration in 4 treatment conditions.

*The secondary outcome measure* consists of studying the differences between baseline oxytocin concentration between healthy subjects and ASD. T-tests will be conducted to determine the difference between two groups.

In this protocol, we have thought of several exploratory or secondary aims that include to compare brain function and functional connectivity between healthy controls and patients with ASD in response to resting state, in response to social cues and in response to interactive social games. We will also investigate the differences in behavioral and physiological responses between ASD and healthy subjects. We will also investigate differences between these two groups (during placebo administration) in baseline plasma OXT concentration, metabolome and exposome and cytokines levels.

In our exploratory analysis, we suggested to study the different factors that could explain heterogeneity in ASD such as clinical dissociation (different kinds of social deficits), behavioral and genetic and epigenetic contribution. We will conduct separate correlation analysis for each of these aims with the severity of ASD and brain function differences with controls. It is also possible to conduct factor analysis to study which behavioral variable for instance best predict ASD severity in clinical and brain function. The same applies for the best predictors of target engagement. We believe that not all patients with ASD will benefit from IN-OT. Hence, we will study the genetic factors, epigenetic factors, clinical classifications and behavioral patterns in determining TEE-OXT or OXT-effects.

It is possible that we publish separately target engagement results (comparison between doses of OXT) and oxytocin effects (24 and 48 as compared to placebo) on the same tasks that are conducted inside the MRI scanner.

Withdrawals, missing data and ineligible patients will be stated. Data will be controlled and double checked by the PI before publishing papers. Outliers will be investigated with statistical tools. Post-analysis will be checked for quality and checked for confounder factors, covariates. Additional precision on the type of analysis (behavioral, physiological and brain) will be submitted as amendments once the PI and staff members start working on the analysis of the data of the project.

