**Aim 4: Plasma oxytocin concentration and exposome/metabolome**

Here we hypothesize that IN-OT will enhance plasma oxytocin concentration in a dose dependent fashion.

Primary outcome measure: We will investigate the differences between treatment conditions in oxytocin plasma concentration. We expect to find that higher doses of IN-OT will enhance significantly the plasma OXT concentration as compared to lower dose of IN-OT and to placebo.

Secondary outcome measure: We will study the differences between healthy subjects and patients with ASD in terms of baseline oxytocin concentration. We expect significant difference and reduced levels of OXT at baseline in ASD.

different nature of social dysfunctions.

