- **Vital signs:** Prior to hormone administration, temperature, heart rate and blood pressure will be measured and recorded by the CRN nurses. Weight and height will be also measured. If heart rate is above 100bpm, or blood pressure is above 140/90, vitals will be re-measured. If levels remain elevated after 3 successive recordings in both limbs (total of 6 recordings) measured at least 5 minutes apart, the study physician will be notified and asked to advise on how to treat the subject and whether it is safe to continue with the protocol. Subjects may still be included at the discretion of the study physician. This is done in order to proceed with baseline vital signs that are within post-hormone administration guidelines. Researcher will ask if the subject is experiencing any adverse events at this time, to provide a baseline before hormone administration.
- **Blood draw:** A registered nurse from the CRN will collect 10 ml of blood by venipuncture for subsequent baseline measurement of plasma oxytocin. Blood will be collected in a lavender-top EDTA-treated tube. Samples will be immediately centrifuged at 4C by the CRN core laboratory and the plasma and blood cells will be stored at -80 until assay at the CRN unit.

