- **Blood draw:** 5 minutes after spray intake, a registered nurse from the CRN will collect 10 ml of blood by venipuncture for subsequent baseline measurement of plasma oxytocin. Blood will be collected in a lavender-top EDTA-treated tube. Samples will be immediately centrifuged at 4C by the CRN core laboratory and the plasma and blood cells will be stored at -80 until assay.
- **Vital signs:** 15 minutes after spray intake, temperature, heart rate and blood pressure will be re-evaluated by the CRN nurse to check for any side effects of IN-OT. There are several pieces of evidence of safety and absence of side effects from chronic and acute intake of IN-OT. Thus, we do not expect any side effects from the hormone oxytocin intake. However, we will ask subjects if they feel any side effects. If no side effects are reported, but temperature has increased or decreased more than 2 degrees, heart rate is above 100 bpm, or blood pressure is above 140/90, the vitals will be re-measured. If levels remain elevated after 3 successive recordings in both limbs (total of 6 recordings) measured at least 5 minutes apart, the study physician will be notified and asked to advise on how to treat the subject and whether it is safe to continue with the protocol. Subjects may still be included at the discretion of the study physician. If subjects were to experience a serious adverse event, such as a heart attack or an anaphylactic reaction, a code will be called and, if necessary, the subject will be taken to the Emory ER. [name] or/and [name] and the CRN nurses will be notified by the experimenter. [name] or [name] will call to admit the subject to the ER. As we already mentioned, it is not likely that oxytocin has any side effects based on the growing evidence in the literature. In addition to vital signs, we will ask participants if they feel any side effects.

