## Specimens

3 Saliva samples will be collected for DNA analysis. We will use the Oragen DNA kits. Some samples might be used to quantify DNA methylation of OXTR and OXT gene or OXTR polymorphisms, MET gene. The remaining samples will be kept safe for potential future use. We will not collect saliva samples from healthy subjects.

8 blood samples (EDTA purple tubes of 10 ml each) will be collected per subject for all 4 MRI visits (4 blood samples will be collected before intranasal administration and 4 blood samples will be collected after oxytocin administration for all visits). Samples were kept chilled in ice and centrifuged within 1 h from collection at 1600 g for 15 min at 4 °C. Plasma was removed and initially frozen at -20 °C, then stored at -80 °C. Plasma samples and blood cells will be extracted and stored at -80 °C until the assays were performed. The centrifuging will be performed at

ACTSI and the samples will be stored at CRN until we are ready to transport some of the samples for the different laboratory to analyze it.

We intend to send some aliquots of plasma from each of these 8 samples to public health to quantify oxytocin concentration in the plasma and to quantify the exposome and metabolome (chemicals/pesticides).

Plasma will be analyzed for cytokines levels.

Blood cells from 4 blood samples (prior to OXT administration) will be sent to analyze the DNA methylation and/or to analyze OXTR polymorphism analysis.

The rest of blood cells and plasma will be kept safe at CRN unit for future analysis.

All these specimens are collected from healthy subjects and from patients with autism.

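### The primary plasma oxytocin analysis uses post-spray samples only and forgoes the precision that the planned same-visit pre-spray samples could add

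*Combined protocol and SAP*

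**What the plan says.** The objective, under Aim 4 of the Objectives, is a comparison between conditions: "We will investigate the differences between treatment conditions in oxytocin plasma concentration". The matching analysis is under aim 5 of the Statistical analysis section. It restricts the data ("Samples of post-administration of IN-OT will be analyzed") and names the model: "We will conduct ANOVA repeated measures on the different OXT concentration in 4 treatment conditions". It names no baseline, change score or covariate.

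The samples for a baseline are in the plan:

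- In the section on the second visit, before the spray: "A registered nurse from the CRN will collect 10 ml of blood by venipuncture for subsequent baseline measurement of plasma oxytocin".
- In the same section, after the spray: "5 minutes after spray intake, a registered nurse from the CRN will collect 10 ml of blood by venipuncture". This bullet also calls its sample a baseline measurement, so the two labels need reconciling.
- Table 2 marks a pre and a post sample at all four scan visits.
- The Specimens section counts them: "4 blood samples will be collected before intranasal administration and 4 blood samples will be collected after oxytocin administration for all visits". It states the intention to measure oxytocin in aliquots of all eight.

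The only stated uses of the baseline concentration are the secondary t-test of ASD against healthy subjects and the related exploratory group comparison.

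**The concern.** The hypothesis is that the spray raises plasma oxytocin in a dose-dependent way. The natural reference for each post-spray value is the same patient's level shortly before the spray on the same day. A repeated-measures ANOVA removes stable differences between patients. It does not remove movement in a patient's own level between visits about a week apart, and that movement is part of the error against which doses are compared.

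The plan sees this problem elsewhere. For resting connectivity (aim 1) it notes that no baseline is acquired and adds modelling steps to account for visit-to-visit fluctuation. For plasma the baseline is acquired and then left out. Visit order is a covariate in the primary analyses of aims 1 to 3 but is not named for plasma.

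At stake is the precision of the dose comparison. It matters more if enrolment ends at 30 or 40 patients rather than 50, which the Randomization and blinding section allows.

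**Working it through.** **Plan's own figure.** The plan gives no power figure, SD, correlation or expected effect for plasma oxytocin. Its general claim is 50 patients for 95% power at d = 0.2 on one measure. Reading 0.2 as Cohen's f, with four conditions, an assumed between-condition correlation of 0.5 and alpha 0.05, the noncentrality is 0.2² × 50 × 4 / (1 − 0.5) = 16 and power is 92.7%; 55 patients would be needed. The claim is therefore reached only with an unstated correlation. Nothing below depends on it.

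**Inputs.** From the documents: four conditions per patient, one pre/post pair per visit, and N = 50, or possibly 30. Assumed: r, the within-patient, same-visit correlation between pre- and post-spray values, over the range 0 to 0.7, with equal within-patient variance before and after the spray.

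**Formula.** Subtract b times the pre-spray value from the post-spray value. Relative to post-only, the variance of a dose contrast is 1 − 2br + b².

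- Post-only, b = 0: ratio 1.
- Best within-patient slope, b = r: ratio 1 − r².
- Change from baseline, b = 1: ratio 2(1 − r).

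| r | 1 − r² | Cut | 1/(1 − r²) | N = 50 is worth | N = 30 is worth | Change score 2(1 − r) |
|---|---|---|---|---|---|---|
| 0 | 1.00 | 0% | 1.00 | 50 | 30 | 2.0 |
| 0.3 | 0.91 | 9% | 1.10 | 55 | 33 | 1.4 |
| 0.5 | 0.75 | 25% | 1.33 | 67 | 40 | 1.0 |
| 0.7 | 0.51 | 49% | 1.96 | 98 | 59 | 0.6 |

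A contrast with 80% power post-only (two-sided alpha 0.05 assumed) would have about 80%, 83.6%, 89.9% and 97.5% power in the four rows.

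**Simulation of the within-patient slope.** In 4,000 simulated crossovers the variance ratios were 1.007, 0.919, 0.758 and 0.517 at N = 50, and 1.008, 0.911, 0.731 and 0.509 at N = 30. Post-only, adjusted and change-score estimates were all unbiased.

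**The form of the baseline term matters.** Raw pre-spray concentration with only a random patient intercept fits a single slope. That slope mixes the between-patient relation (some patients are high both before and after) with the within-patient one, so b is pulled above r. Simulated ratios at N = 30, for an assumed between-patient SD of 1 or 2 times the within-patient SD:

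| r | Raw, SD 1× | Raw, SD 2× | Patient-mean-centred |
|---|---|---|---|
| 0 | 1.12 | 1.47 | 1.01 |
| 0.3 | 1.00 | 1.15 | 0.91–0.92 |
| 0.5 | 0.80 | 0.90 | 0.75–0.77 |
| 0.7 | 0.52 | 0.57 | 0.50–0.52 |

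At low r the raw form can be worse than the planned ANOVA. Centring restores about 1 − r².

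**Constant r is favourable.** Suppose absorption at 48 IU varies between visits with an SD 1.5 times the within-patient SD (an assumption), and none is present on placebo. With r = 0.7 otherwise, the per-patient variance of that contrast is 2 + 1.5² = 4.25 post-only and 2 × 0.51 + 2.25 = 3.27 adjusted. The ratio is 3.27 / 4.25 = 0.77, a cut of 23% rather than 49%.

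**The case against.** The strongest reply is that nothing is broken. Treatment is randomly assigned, so differences in pre-spray level between dose visits are chance, and the ANOVA standard error already reflects them. That stands. A reader might infer that the post-only analysis is biased, or that it mistakes baseline differences for dose effects in a way that invalidates it. The documents do not support this.

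Second, the size of the gain is unknown and nothing shows that the plasma comparison is short of precision. That also stands, and it keeps this an efficiency point.

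Third, adjustment is not free of conditions. It removes only the part of the visit-to-visit variation that the baseline predicts, and a poorly chosen form can lose precision. The Procedures also expect some procedures to be omitted at visits, and a visit without a pre-spray value drops out of the adjusted model unless this is handled. A reader might suppose that all eight assay results are in hand. The Specimens section states only an intention to send aliquots for assay.

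Fourth, the Statistical analysis section ends by promising a check of covariates and later amendments on analysis detail. This does not commit to the plasma baseline, and choosing adjustment after seeing results is what pre-specification is meant to prevent. It does give a route for the change.

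**Conclusion.** The point holds as a matter of lost precision, not bias. The primary plasma analysis sets aside a same-visit baseline that the plan already collects and intends to assay. With a within-patient baseline term, and r constant across doses at 0.3, 0.5 or 0.7, the variance of a dose contrast falls by about 9%, 25% or 49%, worth about 1.10, 1.33 or 1.96 times the patients. The gain is smaller if absorption varies at higher doses. If r is near 0 there is no gain, and the cost is about one degree of freedom. These figures rest on assumed values of r and on equal pre- and post-spray variance, neither of which the documents give. The change is worth making because it is cheap, but the existing analysis would not mislead without it.

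**What to change.** Amend the aim 5 paragraph of the Statistical analysis section. Specify a within-patient model of post-spray concentration with treatment (placebo, 8, 24, 48 IU), visit number, and the same-visit pre-spray concentration centred on the patient's own mean over visits; fixed patient effects serve the same purpose. Rule out the raw baseline with only a random patient intercept, and the plain change score. Keep the post-only repeated-measures ANOVA as a sensitivity analysis, and state how a visit with a missing pre-spray value is handled.

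Make the change before plasma data are analysed by treatment. The plan breaks the blind at 25 ASD patients and analyses primary outcomes then, so if plasma results have already been seen by treatment, disclose the timing.

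The cost is SAP wording and one or two model terms. No new samples are needed: the section on healthy subjects' screening says the full number of ASD patients has already been tested, and measurement of all eight samples is already intended.

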## **Data and Safety Monitoring Plan**

Pre-clinical visit (visit 1) Participants will perform behavioral tests, fill questionnaires, provide saliva DNA samples and conduct training (see above for more details). The training might occur at the Emory hospital or at the Laboratory of Darwinian Neuroscience (as part of the collaboration with [name], PhD) that is located at the anthropology building at Emory University. Participants with ASD might be able to lay down inside the scanner for training purposes to habituate to the context.

We do not expect any serious adverse event and if any adverse event happened during the first visit. We expect several adverse events:

- 1- Tiredness

2- Moderate anxiety or fear reaction in response to lying down in the MRI scanner for ASD.

Participants will be asked how they feel. However, the PI or the experimenter will make sure to take note of these potential adverse events or any unexpected adverse events. All unexpected adverse events related to the first visit will be reported promptly to the IRB and DSMB. All serious adverse events related or not to the first visit will be reported promptly to the IRB, DSMB and to the sponsor. Serious adverse event (based on FDA documentation) includes: life-threatening adverse event, inpatient hospitalization or prolongation of existing hospitalization, a persistent or significant incapacity or substantial disruption of the ability to conduct a normal life functions, or a congenital anomaly/birth defect). Unexpected adverse event is an adverse event that is not listed in the investigator brochure or is not listed at the specificity or severity that has been observed or is not consistent with the risk information described in the protocol.

Severity grading scale for adverse events will be based on this following chart (FDA-based):

- **Grade 1:** mild: asymptomatic or mild symptom; clinical observations only; no intervention indicated
- **Grade 2:** Moderate: minimal, local or noninvasive intervention indicated, have some effect on daily activity
- **Grade 3:** Severe or medically significant that affects daily activity but not immediately life-threatening; hospitalization or prolongation of hospitalization indicated; disabling.

We do not consider any event as related to the study unless if the participant was on-site at Emory with the experimenter. All events that occurred before participants' arrival and after participants' departure will be considered unrelated.

Clinical visits (4 visits): Each participant will participate in 4 clinical visits at the CRN unit at the Emory Hospital and at BTCI MRI scanner. All the rules below apply for healthy subjects and for patients with ASD.

Based on prior literature, we have a list of expected adverse events that could be linked to oxytocin inhalation or placebo inhalation. This list includes any random symptom that was mentioned in trials previously conducted on single administration of oxytocin and placebo. They are considered random because some of them occurred during placebo spray intake, some of them were not found to be significantly different between placebo and oxytocin, and some of them are mentioned in the medical brochure. The list of expected adverse events includes:

- 1- Nausea or mild nausea
- 2- Vomiting or tendencies to vomit
- 3- Headaches
- 4- Irregularities of the pulse (tachycardia, bradycardia, arrhythmia, very rare hypertension)
- 5- Skin rashes and allergic reactions
- 6- Shortage of breath
- 7- Blood pressure decrease
- 8- Circulatory collapse
- 9- Runny nose

- 10- Tiredness
- 11- Sore throat
- 12- Shakiness
- 13- Sweating
- 14- Coughing

Participants will not be given this list and asked explicitly about it. Instead, the experimenter will ask participants how they are feeling following spray administration.

Participants will be also asked upon arrival on the 2nd, 3rd, 4th and 5th visit if there were any changes in their health.

In this clinical trial, we do not expect serious adverse events, and given that the subject is receiving 3 doses and placebo across 4 different visits (within the same study), we would like to define the terminology of reportable events and a plan to notify the IRB of reportable events:

**Relatedness:** the PI will consider that any event (serious, unanticipated, death, adverse event, not serious) is related to the treatment only if the event occurred internally during the clinical visit after spray intake (4 clinical visits at CRN unit at Emory Hospital and BITCI MRI scanner at the Emory Hospital). Thus, an event is considered as a related adverse event or a related unanticipated event if it occurred during the few hours of testing (up to 4 hours) and will not be considered related to the treatment once the subject leaves the hospital. The PI will take note of all related expected adverse events (list above) in a log document and report them periodically to the sponsor and the IRB during the continuing review. The PI will report promptly any unanticipated problem (not expected, related, and provides a risk to the participant) to the IRB and to the sponsor. The PI will also report promptly any serious adverse event that is related to the spray intake (that occurred on site visits of CRN unit) to the IRB and the sponsor. The PI will also report to the IRB periodically if any serious adverse event not related to the spray but during the period of the study that occurred off site Emory or before spray intake or after the participant left the hospital and between study visits (please see the definition below of unrelated events). The PI prefers to report promptly any unrelated or related serious adverse events to the IRB and to the sponsor with a precision of relatedness to avoid any problems or misunderstanding. The PI will also report serious adverse events to the sponsor ([name]). The serious adverse events include: death, life threatening experience, hospitalization, disability or permanent damage, medical or surgical intervention, emergency seizures.

Written IND safety reports will be submitted to the FDA by the IND sponsor, for serious, unexpected suspected adverse reactions within 15 calendar days of learning of its occurrence. If the event is fatal or is deemed to be life threatening, the report will be made within 7 calendar days. The IND sponsor will also make an assessment of whether the event constitutes an unanticipated problem posing risks to subjects or others (UP). This assessment will be provided to the Emory University IRB, which, in turn will make a final

determination. If the Emory IRB determines an event is a UP it will notify the appropriate regulatory agencies and institutional officials.

**Unrelated events:** If an event happened while the subject is coming to the first visit (before spray intake) or after the subject left the hospital (after spray but not at visit sites) or in between the 4 visits (not at visit sites) and that the subject told the experimenter about it, the event will be considered as an unexpected adverse event but unrelated to the treatment. Some patients might have comorbid anxiety traits or hyperactivity traits or being on drugs (other than oxytocin) and so sometimes these symptoms could underlie the medical baseline condition and are considered not related.

Expected Adverse events (please see the list above)	Unanticipated Problems (related, unexpected and risk to subjects)	Protocol deviations and non-compliance	Serious adverse events (deaths) related and unrelated
Reportable to IRB during continuing review board	Promptly reportable to IRB and DSMB	Promptly reportable to IRB	Promptly reportable to IRB and DSMB with specificity of relatedness
Reported to the sponsor at regular intervals	Promptly reportable to the sponsor	Reported to the sponsor at regular intervals	Promptly reportable to the sponsor
Not reportable to the FDA	Not reportable to the FDA, if not serious	Not reportable to the FDA	Promptly reportable to the FDA by the sponsor

Table 5.

Reportable events for the IRB (regarding the clinical visits).

The sponsor does not require reporting above and beyond IRB requirements.

The PI will review the overall data safety periodically. The PI is actually actively involved in testing participants and will make sure that all adverse events are written down and logged into adverse events templates after testing. Every week, the PI will review the regulatory binder to make sure that all the adverse events and procedures are done accordingly to the protocol. If there is any deviation or any unexpected adverse event or serious adverse event, the PI will report promptly all that to the IRB. The PI will make sure to review the literature on intranasal oxytocin (single doses) periodically and search for any adverse events. If there is any addition in the literature that the PI heard about or read about, she will inform the IRB promptly.

Regarding the plan for site monitoring for data quality and protocol compliance, the PI will review the data after each subject visit and the research coordinator will monitor for protocol compliance and data quality. In addition, we will perform self-monitoring (twice a year) using the EU-Self-monitoring Tool. The PI will meet at regular intervals (once per month) with the sponsor ([name]) to update him about the study and the adverse events. The sponsor will be responsible for ongoing safety evaluation and will inform the PI of new safety information. The PI will inform the sub-investigators and the IRB if she is provided with new safety information. The sponsor will inform the FDA.

Based on the literature and the growing evidence of safety of intranasal oxytocin administration and that prior data suggest that the intervention does not have potential to induce significant risks or toxicity to subjects, we do not think that a DSM or DSMB is necessary. However, the PI has a plan for reporting adverse events and any deviations promptly or periodically based on IRB policies and regulations. We have discussed these reportable events in the section above and table 5.

When the data collection stops, the DSMB and self-monitoring will stop too given that there are no more data that are being collected.

For data analysis, we will be working closely with [name] and her technician [name] here at Emory to process the neuroimaging data.

Human subjects' data to be collected includes 1) DNA from saliva samples for genetic analysis, 2) hormone levels assayed from blood plasma, DNA genotyping from blood cells, immune analysis from plasma, exposome and metabolome analysis from plasma. 3) behavioral responses during computerized tests, during MRI scans, during clinical interviews, questionnaires and forms 3) functional and anatomical brain images, 4) physiological responses such as EDA and HRV, 5) Vital signs. Subject data will be identified by ID number, with only the PI of this study ([name]) having access to the list linking subject names and ID #s. This list will be saved on the Emory server of the department of Psychiatry that is highly secured and protected by my emory login and password. All data will be collected specifically for the purpose of this research project.

Before the end of each year prior to the IND annual report oxytocin, a literature review on single-dose intranasally administered oxytocin studies will be done to assess any new safety information pertaining to the administration of this hormone. The results of this review will be kept in the

regulatory binder, and any discovery of additional adverse effects of oxytocin or any changes relevant to the safety of the subjects will be reported to the IRB and the FDA. Additionally, protocol changes would be made to account for these safety issues based on study physician recommendations. The dates of this review will be kept in the outlook calendar of the project coordinator.

In addition to the above plan, we would like to add that the clinical aspects of the study will be conducted under the auspices of the Department of Psychiatry, which has a well-established procedure to deal with adverse events resulting from our planned studies. All study participants will be evaluated by [name] or [name] or the nurse practitioner before taking the treatment spray. The clinical aspects of the study procedures and assessments will be performed in the Atlanta Clinical and Translational Science Institute (ACTSI) – which is a dedicated research unit housed inside the Emory University Medical Center in the same building which houses Emory Intensive Care Unit, Pulmonary and Critical Care Service and Emory Emergency Room. The ACTSI is staffed by fully trained nurses who are experienced in providing support to NIH-funded studies in all medical specialties. The ACTSI management is highly qualified, consisting of [name], who is a Professor of Internal Medicine and Endocrinology.

The adverse events will be also reviewed by the PI and clinical investigators and also will be reviewed by the Emory Data Safety Monitoring Board (DSMB). All adverse events will be reported annually to the Emory DSMB.

The co-chair of the DSMB is [name] and other clinical researchers who serve as the external DSMB for investigator-initiated clinical trials conducted by Emory researchers in the Department of Psychiatry and Behavioral Sciences.

At least four weeks prior to DSMB meeting, the research coordinator/study staff will prepare a report to be reviewed during that meeting. The report will include the number of participants who signed consent for the study and were randomized, the number of post-randomization dropouts, reasons for these dropouts, and safety concerns, adverse events, etc. An up-to-date consent form will be provided, as well as a summary of measures taken to protect confidentiality (data storage, use of coded ID numbers, etc). The PI will also prepare a report summarizing any new data/evidence that might alter the risk/benefit ratio for participating in the study (such as newly published studies, etc). The PI will report any serious and unexpected adverse events in timely fashion to the Emory DSMB and Emory IRB. Actions taken by the IRB in response to adverse event reports will be immediately reported to the Emory DSMB.

